3. STUDY DESIGN

3.1. Study Schema

Description

This is a single-center, phase I/II, randomized, prospective, double-blinded, placebocontrolled study of FMT in the treatment of active pediatric UC. The primary aim is to assess safety and feasibility of a weekly FMT maintenance therapy. A total of 60 patients with active UC (as defined by PUCAI score of > 9) will be enrolled and randomized to first receive FMT or placebo (study treatment).

For therapy/placebo induction, a retention enema will be administered according to the treatment arm to which the patient is assigned. FMT by retention enema will afford us the best delivery method equivalent to that previously described by Moayyeddi and Kunde (see Background) for engraftment of donor stool using FMT materials available to us. Subsequent administrations will occur as oral, frozen encapsulated inocula/placebo for 7 weeks. After the first 8 weeks, subjects will have the option to continue on study treatment or switch to open-label FMT. Subjects will be followed by telephone to assess adverse events for a total of 6 months after their last FMT dose.

Patient metadata and stool samples will be collected at key time points. The patient-reported metadata collection technique will allow for numerous clinical correlations to be parsed out using the random forest machine learning capabilities of synthetic learning in microbial ecology (SLiME) to identify taxonomic features associated with important clinical parameters.(22)

An initial subset of 10 subjects will be enrolled in the study (will be limited to only those patients 12 years of age or older and to those who have mild to moderate ulcerative colitis) and randomized to receive FMT or placebo. We'd expect short term adverse events to occur within 7 days of FMT administration. Individual subject safety data will be reviewed by the PI to assess whether FMT appears to be safe in the subject before continuing the subject towards open-label use of FMT.

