5.2. Study treatment and procedures

5.2.1. Screening and Enrollment

Patients with active UC that are part of the Boston Children's Hospital Gastroenterology and Nutrition clinic as well as referrals from outside of BCH will be pre-screened for study participation. Potential subjects who agree to participate in the study will have a medical exam with labs to assess eligibility. Participants will also undergo a baseline serologic assessment of HIV, HBV and HCV status within 2 weeks prior to the first FMT dose. Females who have achieved menses will undergo urine hCG testing. These four lab tests are considered for research purposes only.

It is expected that study participants will receive ongoing clinical care at BCH for the duration of the study. Study participants, who self-refer or are referred by a GI provider not at BCH, will have their primary GI provider notified of their participation in the FMT study and follow up clinical care at BCH during the course of the study at planned intervals. The study PI will provide the primary GI provider with contact information to relay any questions and concerns during the study period. At the completion of the subject's involvement in the study, the PI will provide a final written and/or verbal report to the primary GI provider for continuity of care.

Presence of active mucosal inflammatory bowel disease (active colitis) is an eligibility requirement for this study. Subjects with evidence of inflammation in a prior staging colonoscopy completed no more than 105 days will not be required to repeat a standard staging colonoscopy solely for the purposes of research. Subjects who have no evidence of active disease by endoscopic scoring of disease at the time of staging colonoscopy will not be randomized and will be excluded from the study.

An initial subset of 10 subjects will be limited to patients with mild to moderate Ulcerative colitis (i.e., PUCAI < 65) and to individuals ≥ 12 years of age.

Upon confirmation of eligibility and completion of randomization, subjects will receive an induction antibiotic regimen (or corresponding placebo if in placebo arm) for one week to decrease levels of indigenous microflora (Study Day -8 until Day -1).

The antibiotic regimen will include:

1) A double antibiotic capsule containing vancomycin 125 mg and polymixin 62.5 mg to be administered orally (PO) according to the following body surface area (BSA) parameters:

BSA* (m ²)	Capsule	Frequency				
< 0.5	1	3 times a day				

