5.2.3. Open-label FMT or Follow-up

After completing 8 weeks of blinded study treatment, study subjects will be given the option to receive open-label maintenance FMT weekly for the remainder of the study if they initially received placebo and did not improve OR if they received FMT, improved, and wish to continue treatment. Subjects will be considered to have improved if their PUCAI score shows improvement of at least 10 points compared to baseline or a score of 10 points or less.

After a subject receives the last dose of blinded study treatment at week 8, the subject's treatment assignment will be unblinded to determine the appropriate course of action. Those subjects, who 1) are found to have improved after receiving 8 weeks of placebo or 2) are found not to have improved after receiving 8 weeks of FMT, will not be eligible to receive open-label FMT. Those subjects will be considered in follow up and will have disease status assessments conducted weekly for the 1st month and then monthly for the following month or 5 months. Subjects will also collect a stool sample and have medical examinations done at 3 and 6 months after their last dose of FMT.

Study subjects who are eligible and interested in continuing on to open-label FMT can be enrolled within 14 days (\pm 7 days) following blinded treatment completion. For the open label phase, subjects who received active treatment (FMT) will proceed directly to open label treatment weekly capsules. However, subjects randomized to placebo (aka no antibiotics, no FMT) will undergo a 7-day antibiotic conditioning and a 2-day rest period prior to commencing open-label FMT treatment that will begin with a retention enema. Thereafter, all subjects will return weekly for observed FMT administration as previously described, AE assessment and survey and stool collection. Routine laboratory assessments and medical exams will be conducted monthly. At all times during this study, standard of care progression of medical/surgical therapy will be offered if clinical course dictates it is necessary for both FMT and placebo arms of the study.

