5.3.3. Clinical Outcomes

Primary Outcome Measures

- 1. Presence of FMT-related adverse events grade 2 or above.
- 2. Proportion of subjects with any FMT-related adverse events of grade 2 or above at 8 weeks post-FMT. Patient related outcomes of rectal bleeding and number of bowel movements. Rectal bleeding will be assessed using common language from PUCAI scoring. (See Figure 1)

Figure 1.

Rectal Bleeding
None
Small amount only, in less than 50% of stools
Small amount with most stools
Large amount (> 50% of stool content)

Secondary Outcome Measures

- 1. Remission as defined by PUCAI of ≤ 9
- 2. Improvement in inflammatory biomarkers (stool calprotectin, serum ESR/CRP, albumin, Hematocrit).
- 3. Changes in gut microbial composition.
- 4. Improvement of PUCAI of \geq 20 points. (30)
- 5. Assessment of engraftment of donor microbes into recipients.

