6. SAFETY ASSESSMENT

6.1. Adverse Event Assessment and Reporting

Comprehensive assessments of any apparent adverse event(s) (AE) experienced by the study subject will be performed throughout the course of the study.

The PI will submit reports of unexpected Serious adverse events (SAEs) and other unanticipated problems to the Institutional Review Board (IRB) at Boston Children's Hospital and to OpenBiome according to their policies.

The PI will report events that are both serious and unexpected and that are associated with FMT/study intervention to the FDA and other applicable health authorities within the required timelines as specified in 21 CFR 312.32 (IND Safety Reports).

The following unexpected AEs will be assessed, recorded and reported to the Data Safety Monitoring Board (DSMB) on an expedited basis: all SAEs, AEs grade 3 (according to CTCAE 5.0 (31) if applicable) or above, and any unexpected AEs grade 2 or above that is possibly or probably related to FMT (as determined by a blinded investigator). Only an AE that meets the above criteria will be recorded and reported. Each reported AE will be described by its duration (i.e., start and end dates), regulatory seriousness criteria if applicable, expectedness, suspected relationship to the study treatment, and actions taken (a blinded investigator will determine expectedness, severity and relationship to study treatment).

Individual subject participation will be temporarily halted until the DSMB determines appropriateness of re-initiation of therapy in any subject experiencing an adverse event resulting in: an Emergency Department visit that is possibly or probably related to FMT, significant worsening of their disease, or experiences 1 SAE Grade \geq 3.

Individual subject participation in the study will be permanently stopped if a SAE Grade ≥ 3 is deemed possibly or probably related to FMT, including any hospital admission.

If 2 or more subjects experience 1 SAE grade \geq 4, all study activities will be halted until the DSMB determines appropriateness of re-initiation of therapy in any subject.

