7.3. Data Analysis

All patients who are eligible, randomized, and have received at least one-dose of the study medication including antibiotics/placebo in the first week will be included into the analysis for primary outcomes to assess the safety and tolerability of FMT, as this will be a per protocol (and not intent-to-treat) analysis . Continuous variables will be presented as mean and standard deviation (SD) or median and interquartile range (IQR), depending on the distribution of the data. Categorical variables will be presented as number and percentage. Disease severity (PUCAI) and patient characteristics at baseline will be compared between the treatment groups to determine whether or not randomization resulted in balanced groups. Methods of 2-group comparison will include Student's t-test, the Mann-Whitney test, Pearson chi-square test, and Fisher exact test, depending on the distribution of the variable under consideration. The primary outcome of safety will be assessed via a 2×2 cross-tabulation, where the proportion of patients with new incident SAEs or upgrade of existing AEs in the FMT group will be compared to the proportion in the placebo group. Two one-sided tests for equivalence (32) will be constructed and the overall *P* value taken to be the larger of the lower and upper tests. Statistical significance will be assessed at *P*<0.05.

For the second outcome, we will use longitudinal data analysis methods to investigate changes in inflammatory biomarkers including stool calprotectin, stool lactoferrin, serum ESR/CRP, albumin, and hematocrit over the study period. Generalized Estimating Equations will be performed to examine the association between FMT and changes in these biomarkers.

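### The listed primary AE outcome and the AE recording rule turn on relatedness to FMT, so grade 2 reactions to the antibiotic week, which only the FMT arm takes, can go uncounted and unrecorded; sections 7.1 and 7.3 define a different primary endpoint

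*Combined protocol and SAP*

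**What the plan says.** **Exposure.** Randomisation is at Day -8 (5.1). Under 5.2.1, "subjects will receive an induction antibiotic regimen (or corresponding placebo if in placebo arm) for one week". Section 5.2.3 describes the control arm as "subjects randomized to placebo (aka no antibiotics, no FMT"; those subjects get active antibiotics only if they later enter open label.

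**Listed primary outcome.** Section 5.3.3 has two AE items: "Presence of FMT-related adverse events grade 2 or above", with no time window, and "Proportion of subjects with any FMT-related adverse events of grade 2 or above at 8 weeks post-FMT".

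**Analysis set.** Section 7.3 takes eligible, randomised subjects who "have received at least one-dose of the study medication including antibiotics/placebo in the first week will be included into the analysis for primary outcomes".

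**Endpoint in the statistics section.** Section 7.1 bases the primary outcome on new SAEs or worsening of existing AEs after enrolment. Section 7.3 compares the proportion with new SAEs or an upgraded existing AE between arms by two one-sided tests (TOST). Neither sets a condition on cause.

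**Recording and reporting.** Section 6.1 lists, under a heading of unexpected AEs, all SAEs, AEs of grade 3 or above, and "any unexpected AEs grade 2 or above that is possibly or probably related to FMT (as determined by a blinded investigator". It then confines both recording and reporting to events that meet those criteria. Section 8, by contrast, describes a running AE log.

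**Attribution terms.** Section 6.1 uses *FMT* for the grade 2 clause, "events that are both serious and unexpected and that are associated with FMT/study intervention to the FDA" for the regulator, and *study treatment* for describing each AE. Section 3.1 gives that last term as FMT or placebo: "enrolled and randomized to first receive FMT or placebo (study treatment".

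**The concern.** The randomised contrast is a package: antibiotics then FMT, against placebo capsules then placebo. The analysis set treats the conditioning week as study medication, but the listed outcome does not. A filter on FMT-relatedness reads the same in both arms, yet only one arm can suffer harm caused by antibiotics. A subject who stops during conditioning because of a grade 2 antibiotic reaction would sit in the 5.3.3 denominator as event-free.

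The recording sentence in 6.1 makes this harder to repair. A tabulation choice can be changed at analysis; an event that was never recorded cannot be recovered. In a trial whose primary aim is safety and tolerability, that would leave the harm of assignment to the FMT arm incompletely described.

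**Working it through.** **1. Trace an antibiotic-caused event in the conditioning week, FMT arm**

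| Event | Counts in 5.3.3? | Counts in 7.1/7.3? | Recorded under 6.1? |
|---|---|---|---|
| New SAE | No, on a plain reading | Yes | Yes, under the unexpected heading |
| New non-serious, grade 3 or above | No, on a plain reading | No | Yes, under the unexpected heading |
| Existing AE worsening to grade 2, non-serious | No, on a plain reading | Yes | Only if unexpected and possibly or probably FMT-related |
| New non-serious, grade 2 | No, on a plain reading | No | Only if unexpected and possibly or probably FMT-related |

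The last row escapes both endpoint definitions and may escape data capture. The third row counts in 7.3 but may have no record to count.

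**2. Sort the 6.1 and 7.2 triggers by attribution**

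- Limited to FMT: the grade 2 DSMB clause, the Emergency Department limb of the temporary halt, and the permanent individual stop.
- No attribution condition: SAEs and grade 3 or above AEs to the DSMB; the temporary halt for disease worsening or an SAE of grade 3 or above; the study-wide halt for two or more subjects with an SAE of grade 4 or above; and the 5/5 and 7/10 rule in 7.2, which looks at FMT-relatedness only after stopping.

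**3. Reproduce the plan's power figure**

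Inputs from 7.1: 30 per arm, 10% in both arms, margin 0.20.

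- SE = √(2 × 0.10 × 0.90 / 30) = 0.0775
- One one-sided test at 0.05: Φ(0.20/0.0775 − 1.645) = Φ(0.937) = 82.6% (stated: 82%)
- TOST, the test named in 7.3: 2 × 0.826 − 1 = 65.1% by the same approximation; 67.4% by exact binomial enumeration of the Wald TOST

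The second scenario (15%, margin 0.25) gives 85.7% (stated: 85%) for one side, and 71.4% approximate or 69.5% exact for TOST. The stated power therefore matches a single one-sided test. That is a separate matter, but it explains why the baseline below is 67% and not 82%.

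**4. Illustrate the size**

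This supposes that the 7.3 test were applied to the 5.3.3 outcome, which the plan does not say. Assumptions: antibiotic-event rate *a* of 5%, 10% or 20% (not in the documents), independent of other events; a base rate of 10% or 15%, borrowed from 7.1, where it belongs to a different endpoint. The FMT-arm rate with antibiotic events counted is 1 − (1 − base)(1 − *a*). The table gives the exact chance of declaring equivalence.

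| *a* | FMT rate, base 10% | Margin 0.20 | FMT rate, base 15% | Margin 0.25 |
|---|---|---|---|---|
| uncounted | 10% | 67.4% | 15% | 69.5% |
| 5% | 14.5% | 51.2% | 19.25% | 59.5% |
| 10% | 19% | 32.2% | 23.5% | 44.9% |
| 20% | 28% | 8.0% | 32% | 17.8% |

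At a 10% base, the uncounted excess is an expected 30 × 0.045 = 1.35, 30 × 0.09 = 2.7 or 30 × 0.18 = 5.4 subjects in the FMT arm.

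**The case against.** The strongest reply is that the plan's only formal arm comparison, in 7.1 and 7.3, has no attribution filter and runs from enrolment. A conditioning-week SAE or worsening in the FMT arm counts there. This stands. A reader might infer that antibiotic harm is removed from the trial's arm comparison altogether; the documents support that only for the 5.3.3 outcome. Attaching the 7.3 analysis set to 5.3.3 is itself an inference, though a natural one, since 7.3 applies that set to the primary outcomes and 5.3.3 is where they are listed.

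A reader might also infer that every DSMB and halting trigger in 6.1 depends on attribution to FMT. Step 2 of the working shows otherwise: three items do, and the rest, including the study-wide halt, do not.

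Third, FMT-related is not defined as excluding the conditioning antibiotics. The first 5.3.3 item has no window, and the timing in the second could mark the assessment point instead of the start of counting. The assessor is blinded and does not know whether the capsules were active. So some antibiotic events might be attributed to FMT and counted. This softens the claim from certain to a plain reading, but it leaves a primary outcome that depends on each assessor's interpretation.

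Fourth, an FMT-specific outcome fits the objective in 2.1 and the investigational agent in 4.1.1. That supports keeping an FMT-only tabulation. It does not support leaving out the rest of what was randomised.

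**Conclusion.** The point holds in this form. The listed primary AE outcome omits, on a plain reading, harm from a component given to one arm only, while the analysis set includes the subjects exposed to it; the omission favours the FMT arm. Sections 5.3.3 and 7.1/7.3 define different primary endpoints. A new non-serious grade 2 antibiotic reaction meets neither and, if expected or judged unrelated to FMT, is not recorded under 6.1. The running log in section 8 conflicts with that rule.

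The direction follows from the one-sided exposure. The size is unknown, because the documents give no antibiotic AE rate. The fall from 67% to 51%, 32% or 8% rests on assumed rates, independence, a borrowed base rate, and a test that the plan ties to another endpoint. It shows sensitivity and is not an estimate for this trial. This should be corrected.

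**What to change.** 1. **One endpoint.** State a single primary safety endpoint in 5.3.3, 7.1 and 7.3, counted in both arms from the first conditioning dose (Day -8) to the end of Week 8. Where relatedness is used, define it as related to any blinded study intervention: antibiotic or placebo conditioning, enema or capsules. Keep an FMT-only tabulation as a supporting analysis.
2. **Recording.** Replace the recording restriction in 6.1 so that every AE of grade 2 or above is recorded, expected or not and whatever its attribution, with separate attribution fields for conditioning and for FMT/placebo. Bring the AE log in section 8 into line.
3. **Terms.** Use one attribution term in 6.1 for recording and DSMB reporting, in place of *FMT*, *study treatment* and *FMT/study intervention*.
4. **Halt and stop passages.** The sponsor must reconcile those that depend on relatedness to FMT with the rest of 6.1. No clinical rule is proposed here.

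Cost: wording in 5.3.3, 6.1, 7.1, 7.3 and 8, extra attribution fields on the AE form, and more AEs to record. No visits are added, since 5.1 already has AE assessments on Days -8, -1 and 0. The FMT-arm rate may look higher because expected antibiotic effects are included; the FMT-only tabulation puts that in context. If the single endpoint differs from the one in 7.1, the power statement there has to be redone for it.

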3.2.1. Inclusion Criteria

Male and female children and young adults, aged 5 years to 30 years, who meet the following inclusion criteria, will be enrolled in the study.

An initial subset of 10 subjects will be limited to patients with mild to moderate ulcerative colitis (i.e., PUCAI < 65) and to individuals ≥ 12 years of age. If FMT appears to be safe in this subset of patients after 8 weeks in the study (to be assessed by a Data Safety Monitoring Board), expanded enrollment as is described above will occur.

All patients must satisfy below criteria:

- 1. Have UC (PUCAI >9) and have failed, are intolerant to, or have refused first-line maintenance therapy.
- 2. Have had visual or histologic evidence of inflammation confirmed through colonoscopy ideally within 90 days but no more than 105 days prior to randomization.
- 3. Have negative test results for Hepatitis B (HBV), Hepatitis C (HCV), and Human Immunodeficiency Virus (HIV).
- 4. Have a negative urine hCG test if female of childbearing potential.
- 5. Able to swallow antibiotic, FMT or placebo capsules.
- 6. Able to give informed consent and/or assent as appropriate (patients 12-17 will be asked to provide written assent, patients 5-11 will be observed for assent or dissent behaviorally, or with verbal/written communication)
- 7. Willing and able to participate in the study requirements, including serial stool collection, survey completion and clinic visits.
- 8. Willing to undergo telephone follow-up to assess for safety and adverse events.
- 9. Must be free of any known food allergy.
- 10. Agrees and willing to have an enema for purposes of induction therapy.

Patients who have disease that has required other medications (including steroids, immunosuppressives, and biologics) will be included.

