3.2.2. Exclusion Criteria

Subjects who fall into any of the following exclusion criteria at the time of screening are not eligible for enrollment into the study.

- 1. Patients in a clinical remission (PUCAI \leq 9).
- 2. Patients with recent (within 4 weeks) dose change of biologics, 5-ASA, steroids or immunomodulators
- 3. Patients considered to have toxic megacolon.
- 4. Patients with a known drug allergy to vancomycin, metronidazole or polymyxin.
- 5. Patients with a history of aspiration, gastroparesis, surgery involving the upper gastrointestinal tract (that might affect upper gastrointestinal motility) or unable to swallow pills.
- 6. Patients with esophageal dysmotility or swallowing dysfunction.
- 7. Patients with known food allergies.
- 8. Patients with positive test results for HBV, HCV, or HIV.
- 9. Female patients with a positive test result on a urine hCG test.
- 10. Patients unwilling or unable to give consent or participate in all study requirements.
- 11. Patients unable or unwilling to receive a retention enema for purposes of induction therapy.

- 12. Patients with recent (within 6 weeks) systemic antibiotic use.
- 13. Patients who have testing consistent with active clostridium difficile.
- 14. Patients with known prior experience with donor FMT.

Research personnel and care providers will be educated about inclusion/exclusion criteria so that only appropriate patients are approached for informed consent. This will reduce the burden of worry for families and patients as to whether they are suitable candidates for the study. Subjects who are found to have no evidence of active disease by colonoscopy will be excluded from the study.

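### The 20-point PUCAI response (secondary outcome 4) is out of reach for subjects who enter at 10 to 19, so the response rate has a ceiling set by case mix at entry

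*Combined protocol and SAP*

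**What the plan says.** **Entry.** Section 3.1 states "A total of 60 patients with active UC (as defined by PUCAI score of > 9) will be enrolled". The first inclusion criterion in section 3.2.1 is "Have UC (PUCAI >9) and have failed, are intolerant to, or have refused first-line maintenance therapy". The only lower limit is the first exclusion in section 3.2.2, "Patients in a clinical remission", meaning a PUCAI of 9 or less. The first cohort adds an upper limit but no higher floor: "An initial subset of 10 subjects will be limited to patients with mild to moderate ulcerative colitis (i.e., PUCAI < 65". Scores of 10 to 19 are therefore eligible throughout.

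**Outcomes.** Section 5.3.3 lists two PUCAI outcomes among the secondary measures. Outcome 1 is "Remission as defined by PUCAI of ≤ 9". Outcome 4 is "Improvement of PUCAI of" 20 points or more. They stand as separate items, and neither has a time point.

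**Analysis.** Section 7.3 specifies longitudinal models (GEE) for the inflammatory biomarkers. It names no method, denominator or baseline adjustment for either PUCAI outcome. Section 4.1.4 describes 1:1 block randomization and does not mention stratification by PUCAI.

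**A separate rule.** Section 5.2.3 defines who has improved when deciding on open-label treatment: a fall of at least 10 points, or a score of 10 or less. That rule is not an efficacy outcome.

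**The concern.** A responder definition should be attainable by every subject in its denominator. Here the entry floor is 10 and the required fall is 20, so part of the eligible population is fixed as non-responders at enrolment, in both arms. The reported response rate would then partly describe how severe the disease was at entry. Without stratification by PUCAI, the share who cannot respond may also differ by chance between two arms of 30.

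Outcomes 1 and 4 are the only listed secondary measures of clinical disease activity. A reader will want to take them together, yet a subject in full remission may be a non-responder.

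**Working it through.** The plan states no rate, sample size or power for this outcome, so there is no figure of its own to reproduce. The check starts from the definitions.

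**Inputs from the documents.** Entry score B of 10 or more (sections 3.1, 3.2, 3.2.1 and 3.2.2). Response: B − F of at least 20, where F is the final score (section 5.3.3). Remission: F of 9 or less (section 5.3.3). Arms of 30 and 30 (section 7.1).

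**Assumption.** The lowest possible score is 0; any non-negative scale gives the same result for entry at 10 to 19.

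**Step 1: who can respond.** Response needs F ≤ B − 20. For B from 10 to 19, B − 20 runs from −10 to −1, so no possible final score qualifies. The lowest entry score that can respond is 20, and then only with F = 0.

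**Step 2: remission without response.** This is possible whenever B − 20 is below the highest attainable remission score.
- In single-point steps the highest remission score is 9. B − 20 < 9 gives B ≤ 28, so it can happen from every entry score from 10 to 28 (25 to 9 is a fall of 16).
- In 5-point steps the highest remission score is 5. B − 20 < 5 gives B ≤ 20, so it can happen from 10, 15 and 20: 10 to 0 or 5, 15 to 0 or 5, and 20 to 5. From 25, a final score of 5 is already a 20-point fall.

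The documents do not say which step applies. Entry at 10 to 20 is affected either way.

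**Step 3: ceiling and dilution.** Let f be the share entering at 10 to 19, and let pT and pC be the response rates among those entering at 20 or more. If all subjects are in the denominator:
- observed rate = (1 − f) × p, so the ceiling is 1 − f
- observed difference = (1 − f) × (pT − pC), if f is equal in both arms
- ratio of rates = pT / pC, unchanged if f is equal in both arms

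**Step 4: illustration only.** Neither f nor the response rates are in the documents. The rates below are assumed for those entering at 20 or more; the test is a pooled two-proportion test, two-sided 5%, 30 per arm.

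| f | Ceiling | Difference, 50% v 25% | Power | Difference, 50% v 20% | Power |
|---|---|---|---|---|---|
| 0 | 100% | 25 points | 52% | 30 points | 69% |
| 20% | 80% | 20 points | 39% | 24 points | 55% |
| 30% | 70% | 17.5 points | 33% | 21 points | 47% |
| 40% | 60% | 15 points | 28% | 18 points | 40% |

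**Step 5: does a composite restore power?** Take a fall of at least 20 points or a PUCAI of 9 or less. Keep 50% v 25% among those entering at 20 or more.
- If low-entry subjects respond at the same 50% v 25%, power returns to 52% for any f.
- If half of them reach 9 or less in both arms, the placebo rate becomes 0.25(1 − f) + 0.50f, that is 30%, 32.5% and 35% at f = 20%, 30% and 40%, against 50% on FMT. Power is then 35%, 28% and 21%, below the 39%, 33% and 28% in the table.

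The composite removes the ceiling, but its effect on power can go either way.

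**The case against.** The strongest reply is that nothing planned depends on this item. It is the fourth of five secondary outcomes in a trial whose primary aim is safety, the sample size rests on safety equivalence (section 7.1), and section 7.3 plans no test of PUCAI response. That stands. A reader might infer from the power figures that the trial is underpowered because of this definition. The documents do not support that: they make no power claim here, and both f and the response rates are assumed. The denominator for this outcome is also unstated, so counting low-entry subjects as failures is the natural reading but not a written rule.

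A reader might also say that outcomes 1 and 4 contradict each other. They do not. Remission is listed in its own right, so a subject going from 15 to 5 is counted there. A large fall and a low final score are different quantities, and meeting one without the other is not an inconsistency. Examples such as 25 to 8 need single-point scoring, which the documents do not establish.

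Finally, a composite has its own weakness: a subject could qualify on a small change, such as 10 to 9 if single-point scores are possible. That stands too, and it is why the composite should not be the only remedy.

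None of this removes the ceiling. Section 5.2.3 shows that an either/or rule was considered for open-label eligibility, but it does not govern the efficacy outcome. A subject going from 15 to 0 has improved under section 5.2.3 and is a non-responder under outcome 4.

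**Conclusion.** The point holds as a defect in the definition of one secondary outcome. Followed as written, with all subjects in the denominator, section 5.3.3 yields a response rate that cannot exceed the share entering at 20 or more, and an absolute difference multiplied by 1 − f when f is equal in both arms. This rests only on the plan's own thresholds and a non-negative scale.

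The size is unknown because the documents give no baseline PUCAI distribution. If nobody enters at 10 to 19 there is no ceiling, although remission without response remains possible from an entry score of 20. It is worth correcting because the cost is negligible, but it is no threat to the trial's main conclusion: the primary safety analysis and the sample size are untouched.

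**What to change.** In sections 5.3.3 and 7.3:

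1. Compare Week 8 PUCAI between arms, adjusted for baseline PUCAI. Name which pre-treatment survey is the baseline; section 5.1 schedules them at screening, day −8, day −1 and day 0. This analysis has neither the ceiling nor the small-change weakness of a composite.
2. Define the Week 8 responder outcome as a fall of at least 20 points or a PUCAI of 9 or less, so that every eligible subject can meet it.
3. Still report the 20-point fall alone, with its denominator limited to subjects entering at 20 or more.
4. Give the responder outcome a name distinct from the improvement term in section 5.2.3. The open-label eligibility rule itself stays as it is.

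**Cost.** A few sentences and no new data, since PUCAI is already collected before treatment and at Week 8. There are two downsides. The composite is slightly less comparable with reports that use the 20-point fall alone, which item 3 largely covers. A low-entry subject can also qualify on a small change, so the composite may raise or lower power; item 1 guards against relying on it.
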